5.2 Recruitment

Participants will be recruited from the Baylor University and the surrounding communities. This proposed study is planned to provide data for use in a undergraduate research engagement course (BIO 1125) at Baylor University. Citizen science is a growing movement that increases the involvement of everyday people and students in the collection and analysis of data in collaboration with professional scientists. Healthy adult participants will be recruited for this study from the University and surrounding community, as well as from students who express interest in taking this citizen science undergraduate research engagement course. Subjects will not be required to take the course to participate in the study, and students will not be required to participate in the study to take the course.

5.3 Protections for the Use of Students as Research Subjects

Analysis of the proposed research study data will take place as part of a newly redesigned course at Baylor University offered through the Biology Department, and some of the participants will be recruited from the pool of students who express interest in taking this class. De-identified data generated from the research study will be used by the students in the course to learn about computational biology and the microbiome. Identifying metadata such as gender, race, and age will not be shared with the class. [name], this study's principal investigator (PI) and adjunct course instructor, has extensive experience and involvement with other human microbiome projects.

Importantly, participation in this research study and course will present a unique learning opportunity for students to be involved in citizen science. We believe that the students will be highly invested in learning about data analysis techniques and methodology in part because they will be analyzing their own data. We also believe that the act of participating in the research study is an excellent opportunity for the students in the class who are considering careers in biomedical research and medicine.

Our study will include a dietary intervention, students will analyze the complete de-identified dataset, and we plan use the data generated for publication.

Study participates with be provided a mental health resource sheet should they need to seek professional help at any time during the study.

To prevent coercion of the study research participants, the following protections are in place:

IRB # 1845028-2 Version 3 Date: March. 3 2022

ND # 1043020-2 /oreign 2

- 1. Students who express interest in the course during the recruitment period will be able to register regardless of their intent to participate in the study. Prior to the start of class, students will be informed that the class will use data generated from this study. They will be offered the opportunity to participate in study as well as a copy of the consent form. They will be asked to provide informed consent for the research study before the beginning of the course.
 - Students who do not consent to take part in the research study or who are excluded from participating in the research study will still be given permission to take the class.
 - b. Study participation will be open to all members of the University community and public who are not interested or eligible to take the course.
- 2. Gathering of informed consent will be completed by a study staff member and not the study PI/course instructor.
- 3. The study PI/course instructor will be blinded to the identity of the participants in the study until completion of the course to prevent any bias in grading.
 - a. Students will not be graded for their participation in the research study and their completion of the study will not affect their success in the course.
- 4. Students will not be compensated for their participation in the research study and will receive no direct benefits from participation.
- The course will be elective.

All data generated from the research study will be de-identified before use in the class. Individuals who choose to participate in the research study can elect to receive a personalized report about their microbiome composition and dietary intake. This report will be generated at the end of the course after final grades have been distributed to keep all potentially identifying information private throughout the duration of the course. If a student completes the research study and then drops the course they may still elect to receive their personalized report. Standard Baylor University policies for dropping courses will still apply to the academic portion of the course.

6 **Study Procedures**

6.1 Demographics and Anthropometrics

At visit 1, basic demographic data will be collected including age, gender, race/ethnicity, and medication use. Participant weight will be measured to the nearest kg and height will be measured to the nearest cm at using an electronic scale and wall mounted tape-measure. Body composition will be measured using the InBody device, which is a bioelectrical impedance device that measures percent body fat and lean muscle, and has been used by [name] in other IRB approved studies at Baylor University. For students and study participants who have mental or physical issues where this would not be appropriate, such as a history of eating disorders, the option to just provide self-reported height and weight will be offered.

IRB # 1845028-2 Version 3 Date: March. 3 2022

6.2 Fecal Sample Collection

Fecal collection will be completed by self-sampling. Self-sampling has proven to be highly successful based on [name] American Gut Project collaboration utilizing self-sampling of fecal material from 7,000 individuals.²² The participant will be trained on the self-sampling procedure after providing consent at visit 1. Briefly, the participant will collect a small quantity of fecal material using a provided collection kit once per day during each day of the study that they produce a stool. Participants will be instructed on proper sample storage until the sample is returned at a study visit.

To avoid room-temperature storage bias, students and members of the University community who participate in the study will be asked to drop off samples daily at one of two on-campus locations. Stools samples will be stored at -80 within 24 hours of drop off. Participants who do not visit the University campus each day will be given FedEx stamped addressed envelopes and asked to drop samples in the mail daily. The FedEx labels will be for 24 hour delivery using special type B labels intended for use with biospecimens. Further, these stool collection kits and methods are the same methods used with the American Gut Project kit and study (N=15,096), which conducted extensive temperature bias controls (McDonald et al. mSystems, 2018).

We anticipate that not all participants will pass a stool each day. Participants who do not pass a stool each day, will be asked to record their dietary intake normally for that day, but to skip the stool collection and to return an empty collection kit for the day(s) they do not pass a stool.

6.3 Dietary Record Keeping

The DHQIII utilized for the study will be the version that takes account of the subject's dietary history one year prior (with portion size) to study entry; the online tool DHQIII was created by the National Cancer Institute. The daily dietary questionnaire will be based on a 24-hour dietary recall. Participants will record everything they eat and drink each day during the study. Each participant will undergo training to complete dietary records at visit 1 after providing consent. Participant training will include encouragement to actually measure foods eaten using measuring spoons and cups whenever possible. Participants will record their intake using 24hour dietary recalls with an online tool (Automated Self-Administered 24-Hour Recall [ASA24]-2016. Bethesda, MD: National Cancer Institute). The ASA24 is based on the United States Department of Agriculture's (USDA) Automated Multiple-Pass Method (AMPM), which has been validated. The ASA24 system provides secure, password-protected diet entry for participants and de-identified, password-protected data access for researchers. The system does not ask for or store any personal identifying information. Dietary records will be analyzed for nutrient content using the ASA24-generated output which is based on the USDA Food and Nutrient Database for Dietary Studies (FNDDS). From the DHQIII, the Healthy Eating Index (HEI-2016) will be calculated, which is used to determine of the overall diet quality. The HEI is calculated based on 12 components which each have an individually assigned score to give a maximum score of 100. Those individuals having a score above 80 are considered to have a healthy diet,

IRB # 1845028-2 Version 3

whereas those below 50 are considered to have a poor dietary intake, and do not meet 75% of the recommended dietary allowances.

6.4 **Dietary Supplement Intervention**

The recommended dose of vitamin D for adults is 600 IU/day and has an upper limit of 4000 IU/day, with clinical intervention to replete deficiency being 50,000I IU/day. We have set our dose at the upper daily limit, established by the Institute of Medicine, since this study is not mean to replete a clinical deficiency. The supplement will be provided as Nordic Naturals vitamin D3 gummies, which have been certified by a third party with Good Manufacturing Procedures. For these gummies, 4 gummies will provide 4000 IU of vitamin D3. Subjects will consume 4 gummies at the largest meal of the day for 12 weeks. Subjects who are assigned to the placebo group will be provided with placebo gummies, Yum Earth Organic Vegan Fruit Snacks, which have the same composition as the supplement but no vitamin D3. Both will be put in bottles without manufacture labeling so as to disguise the vitamin D from placebo. If for any reason we are not able to get these placebo products, we have the ability to print 3D molds and make our own placebo gummies, which we have done before in our food lab. See Table 1 for list of ingredients.

Table 1. Ingredients list of vitamin D3 and placebo supplements							
	Vitamin D	Placebo					
Ingredients	vitamin D (cholecalciferol)	Organic rice syrup					
	Organic tapioca syrup	Organic cane sugar					
	Organic cane sugar	Pectin					
	purified water	Citric Acid					
	pectin	Ascorbic Acid					
	citric acid	Natural flavors colored with					
		organic concentrate (Apple,					
		carrot,					
		pumpkin,blackcurrent)					
	furamic acid	Organic sunflower oil					
	natural flavor	Organic carnauba wax					
	sodium citrate dihydrate						
	fruit and vegetable juice (color)						
Allergens	Gluten Free	Vegan					
	Contains milk derivatives	Gluten Free					
	Non-GMO	Non-GMO					

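### The placebo is described as identical to the supplement apart from vitamin D3, but Table 1 lists other differences, so the arm contrast alone cannot attribute a microbiome shift to vitamin D

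*Combined protocol and SAP*

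**What the plan says.** Section 6.4 (Dietary Supplement Intervention) names a commercial vitamin D3 gummy as the active product and another brand's fruit snack as the placebo, and says of the latter: "which have the same composition as the supplement but no vitamin D3". On exposure it says: "Subjects will consume 4 gummies at the largest meal of the day for 12 weeks". If the placebo product cannot be obtained, the team may mould its own gummies; no recipe is given.

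Table 1, in the same section, lists the ingredients side by side. The active column includes "Organic tapioca syrup" and "sodium citrate dihydrate". The placebo column includes "Organic rice syrup", "Organic sunflower oil" and "Organic carnauba wax". In the allergen row, only the active product has the entry "Contains milk derivatives", and only the placebo is marked vegan.

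Aim 2 (Section 2.2) looks for changes in the microbiome and in CRC risk factors that are caused specifically by taking vitamin D supplements. Section 4 plans a test of the null hypothesis that vitamin D does not affect the microbiome. Its primary outcome also covers the relation of the microbiome to vitamin D intake and serum vitamin D.

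**The concern.** A placebo isolates an active ingredient only if the rest of the product is the same. The sentence in Section 6.4 claims that property, and Table 1 contradicts it. Randomization balances participants between arms but not the contents of the two products. Any ingredient found in only one gummy is taken by everyone in that arm and by no one in the other.

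What is at stake is the wording of the main conclusion. If the arms differ, the cause could be vitamin D, the other ingredients, or both. If they do not differ, a vitamin D effect could have been offset. The protocol itself gives a reason not to wave this away: Section 2.1 notes that diet can alter the microbiome within a day or two, though transiently, and that the influence of small dietary differences is poorly understood. Aim 1, on diet and the microbiome, does not depend on the placebo match.

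**Working it through.** **1. Compare the two columns of Table 1.** Flavour entries are treated as matching and the fruit or vegetable colourings as equivalent.

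| | Ingredients | Count |
|---|---|---|
| Both products | cane sugar, pectin, citric acid, natural flavour, colouring | 5 |
| Active only, besides vitamin D3 | tapioca syrup, fumaric acid (printed 'furamic'), sodium citrate dihydrate, purified water | 4 |
| Placebo only | rice syrup, ascorbic acid, sunflower oil, carnauba wax | 4 |

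Check on the totals: active 5 + 4 + 1 (vitamin D3) = 10; placebo 5 + 4 = 9.

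Purified water is hardly a meaningful exposure difference; without it the count is 3 against 4. The milk-derivative entry is not counted, because it may describe an ingredient already listed. Under either count the statement in Section 6.4 is false. The columns are legible and name different substances, so damage to the table does not explain the conflict, and no other section resolves it.

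**2. Exposure.** 4 gummies a day × (12 weeks × 7 days) = 4 × 84 = 336 gummies per participant. This counts gummies only. Table 1 gives no ingredient amounts and the section gives no gummy weight, so it cannot be turned into a dose of any ingredient.

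**3. What the arm contrast estimates.** Write the expected difference between arms as

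arm difference = net effect of vitamin D and the active-only ingredients − effect of the placebo-only ingredients.

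Every component is fixed by assignment, so the data from the two arms give one number and cannot divide it. If Aim 2 is read generously, so that the supplement includes its own vehicle, the active-only ingredients become part of the intervention. The placebo-only ingredients remain in the contrast.

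**4. Whether another part of the plan separates the components.**

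- *Each subject as own control (Section 4).* The other ingredients are swallowed with the vitamin D, so within-person change carries both. The schedule in Sections 3.1 and 3.2 also starts stool collection on Day 1, together with the gummies, so no stool is collected before supplementation. An earlier sample would still not separate ingredients that arrive together.
- *Adjustment for recorded diet.* It can account for background diet, but not for an exposure that coincides with arm.
- *Associations with serum vitamin D (primary outcome).* They bear on vitamin D itself, but serum levels are not randomized. They can support the arm contrast but cannot replace it.

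**5. The plan's own figure.** Section 4.1 states a detectable change of 1.24 SD in a dominant taxon with 20 per arm. The point does not depend on it: the figure concerns how large a difference can be seen, not what caused it.

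**The case against.** The strongest reply is that no harm has been shown. Table 1 gives no amounts, nothing in the protocol says that any listed ingredient moves a taxon, and the true ingredient effect may be zero. That stands. It limits the point to attribution, but it does not make the sentence in Section 6.4 true or supply the missing evidence that the ingredients are inert.

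A reader might infer the stronger claim that the vitamin D result is biased, or that an inflated error rate can be calculated. The documents do not support this. An ingredient effect would have to be invented, and the result then turns on further unstated assumptions. For example, take 20 per arm, a Mann-Whitney test at an assumed two-sided 0.05/10 = 0.005, lognormal taxa with an assumed log-SD of 1, no vitamin D effect, and an invented ingredient effect of 0.5 raw-scale SD. The chance of a declared difference is about 58% if the shift is additive and about 8% if it is multiplicative. No such figure is relied on here.

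A reader might also infer that the trial can make no causal statement. That goes too far as well. Randomization supports a causal claim about one product against the other; what is unsecured is which component is responsible.

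It can also be said that Aim 2 speaks of supplements and is already partly a product claim. This is fair, but the aim still claims specific causation, the null hypothesis in Section 4 names vitamin D alone, and the placebo-only ingredients are left over under either reading.

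**Conclusion.** The point holds as an error in the text with a consequence for interpretation. Section 6.4 claims a matched placebo, while Table 1 shows 4 active-only ingredients besides vitamin D3 (3 without water) and 4 placebo-only ones. The randomized contrast therefore compares two gummy products. It cannot by itself attribute a shift to vitamin D, and nothing else planned closes that gap by randomized evidence.

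The size and direction of any ingredient effect are unknown and may be zero. This is a threat to attribution, not a demonstrated bias. The conclusion assumes that Table 1 correctly describes the products supplied and that the colourings and flavours are equivalent; if those also differ, the mismatch is larger. The matter should be fixed: the correction is cheap and changes what the trial may conclude.

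**What to change.** 1. **Section 6.4.** Replace the statement of equal composition with: *The placebo contains no vitamin D3 and also differs from the supplement in the ingredients shown in Table 1.*
2. **Section 4, directly after the vitamin D null hypothesis.** Add: *The between-arm comparison is of two products that differ in vitamin D and in the other Table 1 ingredients; attribution to vitamin D alone is a stated limitation, and associations with serum 25(OH)D are non-randomized supporting evidence.*
3. **Section 2.2, Aim 2.** Keep causal language, but at product level, by ending the aim with: *caused by assignment to the vitamin D gummy versus the placebo gummy.*

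The cost is a few sentences and a protocol amendment, with a narrower Aim 2 claim as the downside. Products, visits, samples and sample size do not change. The edits remain possible after enrolment has begun (recruitment was planned from January 2022; this version is dated March 3 2022).

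Outside the core fix: if the in-house placebo is ever used, it would be sensible to record its ingredients and which participants received it, since it could be a third product. A placebo matched on all other ingredients would remove the ambiguity, but is not needed for this correction.

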6.4 Mental Health Assessment

Mental and physical health: Mental health will be measured with several instruments: First, is the College Undergraduate Stress Scale, which assesses life stressors similar to the Holmes Rahe scale, but adapted for college students (Renner & Mackin, 1998). In addition, the Medical Outcomes Study Questionnaire Short Form 36 Health Survey (SF-36; Ware & Gandek, 1998) IRB # 1845028-2

Version 3

will be used to assess general health. This scale is highly reliable with estimates of both physical and mental health typically above 0.90.

Depression and anxiety: will be assessed with the Hospital Anxiety and Depression Scale (Stern, 2014). This scale has been validated in patient populations and general community settings. It is one of the National Institute for Health and Care Excellence (NICE) recommended tools for diagnosis of depression and anxiety.

Perceived Stress Scale: The Perceived Stress Scale(PSS) is a validated scale that measures the degree to which respondents find their lives "unpredictable, uncontrollable, and overloading." Reliability of this scale has been established to be greater than 0.86. As well content, predictive, and concurrent validity have been established for this measurement tool in adolescents and adults (Cohen S, Kamarck T, & Mermelstein R. 1983; Yarcheski A, & Mahon N. 1999)

Alcohol and drug use: We will use the World Health Organization's tool for screening alcohol, tobacco & drug use (Newcombe, Humeniuk & Ali, 2005). This screening instrument is used to assess use of a range of substances including tobacco, stimulants, depressants, hallucinogenics, and opioids.

All of these scales have been used by [name] in previous studies approved by the Baylor University IRB for use in studies with University students.

6.5 Physical Activity

Physical activity will be assessed using the Global Physical Activity Questionnaire (GPAQ), which was designed by the World Health Organization. The GPAQ is a valid measure of moderate to vigorous activity among healthy adults (Cleland et al. 2014). The GPAQ consists of 16 questions that estimate an individual's level of physical activity in 3 domains (work, transport and leisure time). We will used this tool to measure average regular levels of physical activity in our participants.

6.6 Blood Draw

Blood will be drawn by a licensed phlebotomist from a peripheral arm vein at the designated visits through standard sterile methods. At each blood draw, ~15mL of blood of blood will be collected. Participants will be asked to fast for at least 8 hours prior to the blood draw. Participants will remain in a seated position throughout the procedure and be observed for light-headedness, bleeding, and bruising before, during, and after the procedure. If a participant experiences light-headedness they will be given the option to recline or lay down and continue to be monitored until the light-headedness resolves. If the phlebotomist is unable to successfully locate a vein after three attempts, the blood draw will not be completed.

6.7 Follow-up

Subjects enrolled study may elect to be contacted by telephone, text, or email daily during the data collection period as a reminder to collect a sample, complete a dietary record, and/or to check on their progress.

6.8 Microbiome Analysis

We will use RNA gene sequencing or 16S gene amplicon sequencing or shotgun DNA sequencing as well as novel methods in development relying on sequencing a subset of the fecal microbial RNA or DNA to accurately characterize taxonomic composition of the microbiome.

7 Participant Withdrawal

Participants may withdraw voluntarily at any time.

Participants may be withdrawn from the study by the PI for the following reasons:

- The participant is diagnosed with a disease that may affect their ability to pass feces.
- The study is stopped.

If a subject withdraws from the study, no further data will be collected on the subject. The data that have been collected to that point will continue to be used unless the subjects notifies the PI.

8 Assessment of Safety

